2.5 PERIOD OF STUDY

Recruitment is expected to be completed in January 2024, and sample collection is expected to be completed in September 2024.

2.6 DESCRIPTION OF THE STUDY

2.6.1 VOLUNTEER RECRUITMENT:

The study groups will be formed in accordance with the requirements and inclusion criteria. Each of the subjects will be informed of the purpose and methodology of the project by means of an information document for the volunteer (Appendix II) and must sign the informed consent form provided for this purpose (Appendix III); they may withdraw from participation at any time. The data of the participants will be stored in a clinical history with an individual key number, in accordance with the regulations contained in the current Organic Law 3/2018, of 5 December, on the Protection of Personal Data.

Appointments will be made as follows:

APPOINTMENT 1: A conventional computerised clinical history is taken of the patient, in which data is collected on general health, orofacial and nutritional habits and hygiene. We explain in detail what the treatment consists of: Michigan type relaxation splint (device to prevent tooth wear due to bruxism). Each intervention is governed by scientific and deontological criteria, respecting all the ethical rules of research. The following is a detailed description of the study, its duration and methodology. The four moments of saliva collection will be explained: before, during, and 3 and 6 months after placement, as follows:

-Time 0: the day of the appointment, before the intervention.

-Step 1: On the day of the appointment, device placement.

-Time 2: 3 months after device placement.

-Time 3: 6 months after treatment.

Information and informed consent will be provided.

APPOINTMENT 2: Preparation and taking of models for the Michigan type splint according to the conventional protocol for this treatment.

APPOINTMENT 3: The models will be assembled in the articulator to send and request the making of the splint, specifying whether it is injected or printed.

APPOINTMENT 4: A saliva sample is taken in the device for this purpose. After checking for proper fit and retention, the occlusal adjustments will be made with a handpiece and conventional acrylic and polishing burs. After completion of the procedure, a new saliva sample shall be taken. The samples shall be identified with the patient's assigned code and stored according to conventional standards. An appointment will be made after 6 months to continue with the study and in accordance with the check-up times for correct oral health.

APPOINTMENT 5: The intraoral check-up will be carried out, checking the intraoral health and the state of the splint, with the pertinent adjustments, according to conventional protocol. A new saliva sample will be taken. The patient will be seen after 3 months.

APPOINTMENT 6: The intraoral check-up will be carried out, checking the intraoral and splint health status, with its pertinent adjustments, according to conventional protocol. A new saliva sample will be taken. The sample collection period for this subject will end.

Prior to this, the substances released by the specific material used to make the devices will be identified in the laboratory. The reason for this is the highly dynamic nature of the dental materials market. For this purpose, the solutions will be analysed by liquid chromatography coupled to a mass spectrometer (LC-HRMS). The identification of the compounds present will be based on a non-directed suspect screening approach, comparing the results obtained in the analyses with those already existing for the

RESEARCH PROTOCOL

compounds included in the

list of suspects. This list shall be compiled on the basis of information gathered during the literature review, among other sources. Thus, it shall include from compounds whose presence is expected such as those indicated by the manufacturer, to emerging compounds that could be present due to storage conditions, use, etc. For the identification, statistical and chemometric techniques will be used to establish the correlation between the analytical signals obtained in the LC-HRMS and the information (e.g. masses, structure, mass spectra, etc.) available in bibliography and publicly available spectrophotometric libraries (e.g. Mass Bank). In a second phase, the compounds identified in the first stage will be prioritised according to their level of identification, frequency of detection, toxicity (if known) and availability of analytical standards. Finally, quantification of these compounds will be carried out (figure 1).

[figure not shown]

Figure 1: Timeline *In vitro* study of acrylic-based dental materials: Resting and weathering phase leaching, identification and quantification of released substances EDs and SEP. SAC innovative research group at the University of Córdoba (Spain) that belongs to the Institute of Fine Chemistry and Nanochemistry (IUNAN).

Thus, knowing the possible elements identified, the saliva samples can be treated. This is carried out with a volatile supramolecular solvent spontaneously synthesised by adding hexanol and tetrahydrofuran. The methodology to be followed is the same as previously described in the *in vitro* phase.

Dependent variables: substances of very high concern and endocrine disruptors. Independent variables: usual residence, type of manufacture (printed or injected), time, age, type of polymerisation.

After identification and quantification of the detected substances, the data will be collected in a database with the volunteer's information (ANNEX IV).

Finally, the results will be analysed and correlated with those obtained in the experimental laboratory phase, and the possible participating variables: age, type of material, type of manufacture and habits of the participant (figure 2).

[figure not shown]

Figure 2. Timeline of *in vivo* pilot study on substances released from injected or printed acrylic occlusal splints. University Polyclinic of the European University of Madrid.

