1.3 JUSTIFICATION

This study is framed within the European Community framework on substances that can have an impact on the health and well-being of the population, focusing on their identification, quantification, monitoring and prevention. The population susceptible to treatment of this kind is almost universal. Companies are investing in improvements in this respect, incorporating substitutes to bisphenols, with effects yet to be confirmed, generating a very dynamic and growing market. The literature demands more solid results and improvements in protocols. The Supramolecular Analytical Chemistry (SAC) research group at the University of Cordoba has developed an innovative, sustainable, specific and more economical method based on the use of supramolecular solvents (SUPRAS) combined with high performance liquid chromatography-high performance mass spectrometry (HPLC-HRMS/MS). This method allows the identification of compounds (known and unknown) by covering a wider range of substances present in the materials under study than solvents.

organic waste cannot be dealt with. Given that this method has not yet been implemented in dentistry, despite being amply tested, this pilot study has been developed to lay the foundations of a protocol, and to have a more exact and extensive knowledge of our treatments. One of the most widely used, especially after the pandemic, is the Michigan type acrylic splint, as a treatment for bruxism. It is also a removable device, which is used at least 6-8 hours a day, and does not involve the use of additional plastic materials that could be other sources of additives, such as cements, sealants or dental temporaries, as is the case with fixed prostheses. The population eligible for such treatment must have completed their bone and tooth growth (18 years of age or older). In the present study, two forms of manufacture were chosen: conventional and printed. The reason for not choosing the milled ones is because the latter generate more waste, and their mechanical response as well as the patient's preference are not better. Therefore, identifying the substances released by the acrylics, using SUPRAS and HPLC-HRMS/MS, by contrasting the *in vitro* and *in vivo* results, may shed some light on this issue.

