1.4 OBJECTIVES

There is no evidence of release of substances of particular concern, or endocrine disruptors released from Michigan type acrylic occlusal splints.

General objectives: To describe and quantify the values of substances of very high concern (SVHC) or endocrine disruptors (ED) released from printed or injected acrylic Michigan type splints.

Specific objectives:

1. To identify the SEPs and EDs released by Michigan-type splints made by injection or *in vitro* impression technique, simulating oral environment and wear.
2. Identify SEPs and EDs in saliva released from printed or saliva-injected acrylic Michigan type splints before, during and after insertion in the mouth.
3. To quantify the levels of SEP and ED in saliva released from printed or injected acrylic Michigan type splints in saliva before, during and after insertion in the mouth.
4. Contrast the results obtained in the laboratory test with those recorded in the saliva samples of the *in vivo* study.

5. Relate the results to the manufacturing process, stage of exposure, time, habits and individual characteristics of each volunteer.

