ANNEX IV

Voluntary code	CONCENTRATIONS	CONCENTRATIONS	CONCENTRATIONS	CONCENTRATIONS
	M. Saliva 0	M. Saliva 1	M. Saliva 2	M. Saliva 3
SUBSTANCES				

 Name, surname, ID number and signature of the researcher _____
Date

Sample collection table for each volunteer

VARIABLES	Volunteer 1	Volunteer 2	Volunteer 3	Volunteer 4	Volunteer 5
AGE	-				
GENDER (MALE, FEMALE, OTHER)					
MATERIAL (ACRYLIC)					
MANUFACTURING (INJECTED or PRINTED)		-			
USUAL RESIDENCE (URBAN, RURAL)			-		
EXPOSURE TIME (HOURS) BRUXIST (YES/NO)				-	
REFLUX (YES/NO)					
ANTIDEPRESSANTS (YES/NO)					
ANTIHISTAMINES (YES/NO)					
DECONGESTANTS (YES/NO)					

BIBLIOGRAPHY

- Alhazzawi, T. F. (2016). Advancements in CAD/CAM technology: Options for practical implementation. *Journal of Prosthodontic Research*, *60*(2), 72-84.
<https://doi.org/10.1016/J.JPOR.2016.01.003>
- Alharbi, H. F., Algonaiman, R., Alduwayghiri, R., Aljutaily, T., Algheshairy, R. M., Almutairi, A. S., Alharbi, R. M., Alfurayh, L. A., Alshahwan, A. A., Alsadun, A. F., & Barakat, H. (2022). Exposure to Bisphenol A Substitutes, Bisphenol S and Bisphenol F, and Its Association with Developing Obesity and Diabetes Mellitus: A Narrative Review. *International Journal of Environmental Research and Public Health*, *19*(23).
<https://doi.org/10.3390/ijerph192315918>
<https://doi.org/10.1016/J.ADDMA.2020.101693>
- Bisphenol A and incisor molar hypomineralisation:: A review - Dialnet* (n.d.). Retrieved June 17, 2023, from <https://dialnet.unirioja.es/servlet/articulo?codigo=7998248>
- Carneiro Pereira, A. L., Bezerra de Medeiros, A. K., de Sousa Santos, K., Oliveira de Almeida, É., Seabra Barbosa, G. A., & da Fonte Porto Carreiro, A. (2021). Accuracy of CAD-CAM systems for removable partial denture framework fabrication: A systematic review. *Journal of Prosthetic Dentistry*, *125*(2), 241-248.
<https://doi.org/10.1016/j.prosdent.2020.01.003>

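### Protocol Section 2.6.1 defines the follow-up saliva samples at months 3 and 6, but its appointment list books them at months 6 and 9

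*Protocol*

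**What the plan says.** Protocol Section 2.6.1 states the follow-up times twice under Appointment 1. The introductory sentence reads "The four moments of saliva collection will be explained: before, during, and 3 and 6 months after placement". The list below it repeats "Time 2: 3 months after device placement" and puts Time 3 at 6 months.

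The appointment list in the same section then sets the visits. At Appointment 4 the splint is fitted, with one saliva sample before and one after the adjustments (Times 0 and 1). The next visit is set as follows: "An appointment will be made after 6 months to continue with the study". Appointment 5 takes the third sample and sets the last interval: "A new saliva sample will be taken. The patient will be seen after 3 months". Appointment 6 takes the fourth sample and closes collection for that volunteer.

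Time matters to the analysis. Section 2.6 lists "Independent variables: usual residence, type of manufacture (printed or injected), time, age, type of polymerisation", and specific objective 5 in Section 1.4 is to "Relate the results to the manufacturing process, stage of exposure, time, habits and individual characteristics of each volunteer".

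**The concern.** The definitions and the appointment list cannot both be followed. The appointment list is the sequence that clinic staff would naturally work from, and it contains no month-3 visit.

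Two of the four samples per volunteer depend on it. If visits are booked from the list but results are entered under the Time 2 and Time 3 labels, month-6 and month-9 concentrations would be reported as month-3 and month-6 values. If some volunteers are booked from the definitions and others from the list, one column of results would mix different lengths of exposure, in groups of only 15.

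The results form would not reveal either problem. Annex IV, headed "Sample collection table for each volunteer", has columns for Saliva 0 to 3 but no collection date for each; its only date stands beside the researcher's signature. A month-9 sample would also lie beyond the 6 months of attendance that Annex I requires, so eligibility would not secure the last sample.

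**Working it through.** **Inputs (all from the protocol)**

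- Defined follow-up times: months 3 and 6 (Section 2.6.1, Appointment 1).
- Interval from Appointment 4 to Appointment 5: 6 months (Section 2.6.1, Appointment 4).
- Interval from Appointment 5 to Appointment 6: 3 months (Section 2.6.1, Appointment 5).
- Volunteers: 2 groups of 15, so 30 (Section 2.4); 4 samples each.
- Attendance criterion: 6 months (Annex I).
- Recruitment expected to end in January 2024, sample collection in September 2024 (Section 2.5).
- Daily wear: "which is used at least 6-8 hours a day" (Section 1.3).

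**Step 1: the two schedules, with placement as month 0**

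| Sample | Definition | Appointment list | Shift | Ratio |
|---|---|---|---|---|
| Saliva 2 | 3 | 0 + 6 = 6 | +3 | 6/3 = 2.0 |
| Saliva 3 | 6 | 6 + 3 = 9 | +3 | 9/6 = 1.5 |

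The protocol never writes 9 months; it is the sum of the two intervals.

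**Step 2: is there a reading that reconciles them?** Suppose both intervals run from placement. Appointment 5 then falls at month 6 and Appointment 6 at month 3, so the visits are out of order. Nor can the 6-month visit be a routine check outside the study: it is booked for the study, and the next listed appointment takes a sample.

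**Step 3: samples exposed to the conflict.** 30 × 4 = 120 planned samples; 30 × 2 = 60 are follow-up samples.

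**Step 4: extra exposure.** Taking 3 months as about 91 days, 91 × 6 = 546 hours and 91 × 8 = 728 hours of additional wear before each follow-up sample.

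**Step 5: which schedule fits the calendar?** The protocol gives no fitting dates, so fitting between 1 and 31 January 2024 is assumed.

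| Fitted | Last sample, 3/6 | Against 30 Sep 2024 | Last sample, 6/9 | Against 30 Sep 2024 |
|---|---|---|---|---|
| 1 Jan 2024 | 1 Jul 2024 | 91 days before | 1 Oct 2024 | 1 day after |
| 31 Jan 2024 | 31 Jul 2024 | 61 days before | 31 Oct 2024 | 31 days after |

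The latest fitting date that still finishes by 30 September 2024 is the end of March 2024 under 3/6 and the end of December 2023 under 6/9. Fitting is the fourth appointment, so a volunteer recruited late in January would be fitted later still.

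**Step 6: effect of correcting one number.** With 3 months at Appointment 4, Appointment 5 falls at month 3 and Appointment 6 at 3 + 3 = month 6. Both then match Time 2 and Time 3.

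**The case against.** The mismatch itself is hard to dispute; the case on the other side concerns its consequences.

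- **Labelling.** Section 2.1 requires every sample to be identified by time, among other items, and visits should be traceable in the clinical history. Annex IV also has a row for exposure time in hours. This stands in part: actual dates might be recovered. But the label may mean only the nominal time point, and the exposure row has one cell per volunteer, not one per sample.
- **Intent.** The two written intervals, 6 and 3, are the same two numbers as the defined times, so the drafter may have transposed them and never meant a month-9 sample. That is plausible. It explains the error but does not remove it.
- **Supporting evidence.** Annex I does not say when its 6 months start, and three appointments precede placement. Volunteers fitted by the end of December 2023 could finish a 6/9 schedule on time, and the September date is only an expectation. These points hold, so the calendar and the criterion favour 3/6 but do not prove it. The two explicit statements of 3/6 carry more weight.
- **Size.** All 60 samples would be affected only if staff followed the list for every volunteer and kept the nominal labels. A uniform shift would leave the printed and injected groups compared at equal elapsed times, and no effect on any concentration has been shown. This is right, and the figure is therefore an upper limit.
- **Figure 2.** The in vivo timeline could not be seen. It might show which schedule is meant, but the conflict in the text would remain.

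**Conclusion.** The concern holds. Section 2.6.1 states two schedules that no reading reconciles, and the 6-month interval at Appointment 4 is the outlier. It should be corrected, although it looks like a drafting error rather than a deliberate design.

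Up to 60 of the 120 planned samples could be collected 3 months later than labelled, with about 546 to 728 more hours of wear before each. The upper limit assumes that staff follow the appointment list throughout and use the nominal labels; the hours assume wear of 6 to 8 hours on each of about 91 days. No bias of known size or direction in the concentrations is claimed. The before-and-after pair on placement day is untouched.

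**What to change.** In Section 2.6.1, Appointment 4, change the interval to the next visit from 6 months to 3 months. Appointments 5 and 6 then fall at months 3 and 6, as Time 2 and Time 3 require. In Annex IV, add a collection date for each of Saliva 0 to 3, so that actual time since placement can be calculated and checked. Check Figure 2 against the corrected text.

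Section 2.5 and Annex I need no change on this account. The cost is one number in one sentence and one date field per sample, with no effect on sample size, number of visits or budget.

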2.7 ETHICAL AND CONFIDENTIALITY ISSUES

2.7.1 RIGHT TO BE INFORMED:

Each volunteer will be provided with an information document (Annex II), and informed consent (Annex III), which, once understood, must be voluntarily signed and returned.

2.7.2 COLLECTION AND USE OF BIOLOGICAL SAMPLES

Sample collection will be carried out in accordance with the ethical and legal requirements set out in RD 1716/2011. The containers will meet the requirements according to ISO 6717:2021, and will be packaged and transported according to the protocol Order JUS/1291/2010, of 13 May.

2.7.3 RISKS AND INCONVENIENCE FOR THE PARTICIPANT

The present study does not involve any risk for the patient, as these are procedures and treatments used in everyday dental practice, with a long clinical and scientific history. The discomforts are those inherent to these processes, without any additional discomfort.

2.7.4 ADVERSE EVENTS

It does not imply any additional consideration to those that such treatments may entail.

2.7.5 POTENTIAL BENEFITS

The benefits are those inherent to the treatments indicated: muscular improvements, avoidance of further wear and tear and more severe damage to dental tissue, loss of teeth and mucosal lesions. As an indirect benefit, knowledge of the possible substances detected will provide a better approach to the prevention of possible adverse effects.

2.8 STATISTICAL ANALYSIS

For the descriptive analysis of the variables collected, the mean \pm standard deviation or median [interquartile range] will be used once the distribution has been checked, in the case of the variables collected.

RESEARCH PROTOCOL

quantitative variables. To describe qualitative variables, absolute (n) and relative (%) frequencies will be used and their 95% confidence interval (95% CI) will be calculated.

Chi-square tests (or Fisher's exact tests) will be used to study differences between qualitative variables. In case of quantitative variables, Student's t-test or Man-Whitney U-test will be used, depending on whether they follow parametric or non-parametric behaviour. Binary logistic regression models will be used to determine the Odds ratio (OR) of seroprevalence and its 95% confidence interval (95% CI) to analyse the effect of each variable on the results obtained.

All statistical calculations were performed using SPSS statistical software (version 25.0 IBM Corp.; USA). Statistically significant differences were assumed to exist if the p-value obtained was less than or equal to 0.05.

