The main problem when studying the presence of additives released by dental materials in the organism is the extraordinary difficulty in associating them explicitly to this type of device, given that they are commonly found in our surroundings. Their multiple origins: environmental, nutritional, hygienic sources, etc., make it extremely difficult to associate the origin with the substance identified. For this reason, in vitro studies are a widely used method. However, the protocols developed to date show a certain lack of uniformity: in some, discs are analysed without considering the inhibited layer, in others their polishing does not correspond to the clinical protocol, or there is a lack of uniform extraction ratio, or the solvents are different, or salivary turnover is not taken into account (the possible alterations in its composition, pH, viscosity, or flow that may occur in the same subject, and its role in the chemical erosion of the material). On the other hand, in some of these tests, occlusal wear is not considered. They provide data on quantification and identification of the substances in saliva, mainly bisphenols, substitutes for

and phthalates, in different materials, depending on their manufacturing technique (milled, printed, injected), and their curing (thermo-, self-, photopolymerised). Clinical studies focus on paired samples, or on epidemiological, retrospective descriptive, comparative, retrospective and prospective studies where saliva, blood and urine samples are analysed to determine their assimilation. Among the methodologies used, the FDA (Food and Drug Administration) recommends High Performance Liquid Chromatography (HPLC) or Gas Chromatography (GC). Authors such as Hampe Tristan, advise Mass Spectrometry (MS), or the HPLC/MS tandem, establishing as ideal the combination of High Resolution Mass Spectrometry (HRMS) and MS, since it does not detect products such as Bis GMA, -EMA and -UDMA (De Angelis et al., 2022; Hampe et al., 2022; Kessler et al., 2020; Tichy et al., 2021). (Francisco et al., 2022; Van Landuyt et al., 2011a, 2011b; Vervliet et al., 2022; Wedekind et al., 2021).

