2.3.4 STATISTICAL DATA CONTROLLER

[name] [name] (Methodological and Statistical Advisory Group, Department of Medicine, Faculty of Biomedical and Health Sciences), European University of Madrid.

2.4 POPULATION AND CALCULATION OF THE SAMPLE.

The sample will be obtained from patients who are registered in the database of the Polyclinic of the European University of Madrid, who request a Michigan type splint for the treatment of bruxism, made of acrylic, made in two of the usual ways: printed or injected, in accordance with the inclusion and exclusion criteria shown in Appendix I. As the samples were treated with an innovative methodology in the field of dentistry, such as super solvents, this was a pilot study in which two groups of 15 participants each were formed, depending on the manufacturing process of the splint: injected or printed, totaling 30 volunteers.

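### Section 2.8 names no analysis that adjusts the printed-versus-injected comparison for each volunteer's Time 0 concentration, and does not say whether raw values or changes are compared

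*Protocol*

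**What the plan says.** Section 2.8 sets the analysis of measured quantities in one sentence: "In case of quantitative variables, Student's t-test or Man-Whitney U-test will be used", the choice between the two turning on the distribution of the variable. The only regression model it names is binary logistic. The significance rule is "Statistically significant differences were assumed to exist if the p-value obtained was less than or equal to 0.05", with no statement of one- or two-sided testing.

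The between-group question comes from specific objective 5 in section 1.4: "Relate the results to the manufacturing process, stage of exposure, time, habits and individual characteristics of each volunteer". Section 2.4 gives the size: "two groups of 15 participants each were formed, depending on the manufacturing process of the splint: injected or printed, totaling 30 volunteers".

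The baseline is part of the design. Section 2.6.1 schedules a saliva sample at "Time 0: the day of the appointment, before the intervention", and Annex IV has a concentration column for each of the four samples, Time 0 included. Section 2.1 describes the samples as paired, with each subject serving as their own control. Section 1.2 explains why this is needed: the released substances are hard to attribute to a dental device, "given that they are commonly found in our surroundings". The independent variables listed in section 2.6 are residence, manufacture, time, age and type of polymerisation. Time 0 concentration is not among them.

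**The concern.** Printed and injected splints are worn by different people, so Student's t must take its independent-groups form for this contrast, and Mann-Whitney U always does. Neither test uses the Time 0 value unless the analyst first computes a change, and section 2.8 does not say whether that is done.

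Two things are at stake. First, precision: if raw post-placement values are compared, stable differences between people in background exposure stay in the error term, with only 15 per group. Second, confounding: the protocol text at hand describes no random allocation, so the groups may differ in background. An unadjusted comparison of raw values would attribute part of that difference to the manufacturing process. Leaving raw value or change unspecified also allows the choice to be made after the data are seen.

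**Working it through.** **Plan's own figure.** There is none to reproduce. Section 2.4 gives a pilot size with no power, effect size or standard deviation.

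**Inputs from the protocol.** n = 15 per group (section 2.4) and significance at 0.05 (section 2.8).

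**Assumptions.** Two-sided test; no dropout; log concentrations approximately normal, with equal variance at Time 0 and follow-up; true difference d of 0.8 or 1.0 SD; rho from 0 to 0.9. None of these is given in the protocol.

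**Formula.** Power comes from the noncentral t distribution with noncentrality d / √(2f/n), where f is the variance factor:

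- raw post-placement values: f = 1, 28 df;
- Time 0 as covariate: f = (1 − rho²) × (1 + 1/(2n − 4)) = (1 − rho²) × 27/26, 27 df; the second factor allows for chance baseline imbalance;
- change from Time 0: f = 2(1 − rho), 28 df.

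**Example, d = 1.0.** Raw: 1/√(2/15) = 2.74, power 75% (normal approximation 78%). Covariate at rho 0.5: f = 0.75 × 27/26 = 0.779, noncentrality 1/√(2 × 0.779/15) = 3.10, power 85%. Change at rho 0.5: f = 2 × 0.5 = 1, the same as raw.

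| | rho 0 | rho 0.3 | rho 0.5 | rho 0.7 |
|---|---|---|---|---|
| Power at 1.0 SD, raw | 75% | 75% | 75% | 75% |
| Power at 1.0 SD, covariate | 74% | 78% | 85% | 95% |
| Power at 0.8 SD, raw | 56% | 56% | 56% | 56% |
| Power at 0.8 SD, covariate | 55% | 58% | 67% | 83% |
| Power at 0.8 SD, change | 32% | 43% | 56% | 78% |
| Detectable at 80% power, raw | 1.06 SD | 1.06 SD | 1.06 SD | 1.06 SD |
| Detectable at 80% power, covariate | 1.08 SD | 1.03 SD | 0.94 SD | 0.77 SD |

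**Break-even.** Covariate and raw analyses have the same detectable difference at rho of about 0.20. The change score beats raw values only when rho exceeds 0.5. Over the range examined, rho 0 to 0.9, the covariate analysis is never worse than the change score.

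**In volunteers.** At rho 0.5 the variance reduction alone equals 15/0.75 = 20 per group. With the imbalance factor it is 15/0.779, or about 19.

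**Simulation check.** With 8,000 runs per setting, simulated power agreed with the formulas to within about 1 percentage point, and type I error was 4.7% to 5.4% across the three analyses. Non-detects were not simulated, and the bias from unequal background was not quantified.

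**The case against.** A reader might infer that section 2.8 tests raw post-placement concentrations and discards Time 0. The text does not say so. It names tests for quantitative variables without naming the quantity, and a between-group t-test on change from Time 0 would fit the paired design in section 2.1 equally well. This objection stands. It narrows the point but does not remove it: a change score loses power against raw values whenever rho is below 0.5, and covariate adjustment does at least as well as a change score over the range examined.

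A reader might also infer that the lost power is free to recover. That is not supported either. Rho is not given, the gain at rho 0.3 is only 2 to 3 points, and below about 0.2 there is a small loss. The substances sought in saliva come from laboratory screening of the splint material, so some may be rarely detected before placement and have little usable baseline.

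The study is a pilot with descriptive general aims and no power target, so no stated figure is wrong. That is true, but the protocol does name significance tests and an objective on manufacture, and confounding by background does not depend on a power target.

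Covariates are often left to a statistical analysis plan, and naming a family of tests does not forbid adjustment. Finer details can indeed wait. Here, though, the protocol itself fixes the tests, and those named do not carry through the within-person control on which its design rests.

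Finally, a log-scale model treats background and release as multiplicative, whereas they may add; and one noisy saliva baseline removes imbalance only in part. Both caveats stand.

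**Conclusion.** The point holds in limited form. Section 2.8 does not say how Time 0 enters the printed-versus-injected comparison and names no baseline-adjusted method, although the measurement is taken from everyone and background exposure is the protocol's own stated difficulty. The documents do not establish that raw values will be compared, nor that adjustment must raise power.

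Relative to a raw comparison at 1.0 SD, adjustment changes power by about −1 point at rho 0, +3 at 0.3, +10 at 0.5 and +20 at 0.7. These figures rest on the assumed rho, approximately normal log concentrations, complete follow-up and a usable Time 0 value; many non-detects would shrink the gain. Protection against background imbalance is a second reason to adjust, but it is partial. The protocol should be corrected on this point, though the omission does not undermine its descriptive aims.

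**What to change.** In section 2.8, state that printed and injected splints are compared at each post-placement time by a linear model of log concentration on manufacture, with the volunteer's log Time 0 concentration as covariate. Report the adjusted geometric mean ratio with its 95% CI.

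Set two rules before the data are seen:

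- one treatment of values below the detection limit, for example a fixed substituted value plus a detected/not-detected indicator at Time 0;
- a detection-frequency threshold at Time 0 below which the unadjusted comparison is used for that substance.

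Add Time 0 concentration to the independent variables in section 2.6.

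Cost: a few sentences, no new samples and a little more analysis work. The Time 0 covariate uses one degree of freedom and loses about 1 point of power if Time 0 proves unrelated to follow-up; a detection indicator, if used, takes one more.
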